#### **6.2.5. OS**

The analysis of OS will be similar to that for duration of response just described.

The OS will be analyzed in the modified as-treated population and as-treated population separately.

#### **6.2.6. Pharmacokinetics**

PK profiles of bosutinib will be determined using a sampling regimen and population PK analysis approach. A total of 4 PK samples per patient will be drawn. All patients in the bosutinib treatment group will provide pre-dose blood samples on Day 1, 28, 56 and 84.

Concentrations of bosutinib will be determined in plasma using a Sponsor-approved and validated liquid chromatography/tandem mass spectrometry (LC/MS/MS) assay.

The objectives of the population PK analysis are 1) to develop a population PK model which describes the PK of bosutinib in this patient population, 2) to evaluate the influence of demographic and clinical covariates on the exposure of bosutinib, and 3) to explore the relationship between trough concentrations of bosutinib with clinical safety (drug related adverse effects such as GI AEs, and any other major AEs) and efficacy endpoints.

The concentration of study drug will be analyzed using population PK methodology. Population mean values of PK parameters (eg, clearance [CL/F], volume of distribution [V/F]) will be estimated. PK relationships between plasma study drug concentration and selected outcome measures will be characterized using a population approach.

Details of analysis of PK endpoints is referred to “B1871048 Pharmacokinetic Analysis Plan”, which is separately developed.

### **6.3. Other Endpoint(s)**

#### **6.3.1. MMR at Each Pre-Specified Visit**

Measures of MMR at 3, 6, 9, 12 and 18 months will be evaluated by frequency tables. The two-sided 90% CI will also be calculated.

These analyses except for the MMR at 12 months will be performed using the modified as-treated population and as-treated population, respectively.

The exploratory MMR analysis at 12 months will be analyzed for the as-treated population.

The MMR at 18 months will only be summarized at the FA (refer to [Section 7.2.3](#) with respect to the FA).

#### **6.3.2. Molecular Response**

Measures of MR^1, MR^2, MR4.0 and MR4.5 at each pre-specified visit will be evaluated by frequency tables. The two-sided 90% CI will also be calculated.

Pre-specified visits for MR^1 and MR^2 are 3 and 6 months, respectively, while pre-specified visits for MR4.0 and MR4.5 are 3, 6, 9 and 12 months.

These analyses will be performed using the modified as-treated population and the as-treated population, respectively.

#### **6.3.3. Time to MMR, CCyR, MR4.0 and MR4.5**

The time to response (MMR, CCyR, MR4.0, and MR4.5) is measured from first dose to the first date of response. The time to response will be analyzed using the cumulative incidence method. Yearly rates and percentiles will be displayed. In the analysis of cumulative incidence (see [Section 5.2.3](#)), the competing risk is defined as treatment discontinuation without response. Also, other patients without response will be censored at the last valid assessment for the respective endpoint.

The time to response will be also summarized by descriptive statistics among responding patients.

The time to MMR, MR4.0 and MR4.5 will be analyzed for the modified as-treated population and as-treated population separately. The time to CCyR will be calculated using the modified as-treated population.

#### **6.3.4. Cumulative CHR**

Evaluations of cumulative CHR will be assessed using the frequency tables. The two-sided 90% CI will also be calculated.

The cumulative CHR will be analyzed for the modified as-treated population and as-treated population separately.

Investigators should assess hematologic response according to the original definition of CHR (see [Appendix 1.4](#)). In a statistical analysis, some restrictions (see table footnotes in [Appendix 1.4](#)) are adopted in addition to the original definition.

#### **6.3.5. Time to Transformation to AP and BP CML**

The analysis of the time to transformation to AP and BP CML will be similar to that of the time to response described above.

The time to transformation to AP and BP CML is defined as the time from first dose to the first date of transformation to AP or BP CML. The transformation to AP and BP will be counted while a patient is on treatment up to 28 days after last dose. In the analysis of cumulative incidence (see [Section 5.2.3](#)), the competing risk is defined as treatment discontinuation without transformation. If transformation has not occurred, the patient will be censored at the last valid hematologic assessment.

Investigators should assess transformation to AP/BP according to the original definition of AP/BP CML (see [Appendix 1.3](#)). In a statistical analysis, some restrictions (see table footnotes in [Appendix 1.3](#)) are adopted in addition to the original definition.

Time to transformation to AP and BP CML will be analyzed for the modified as-treated population and as-treated population separately.

#### **6.3.6. Mutations**

Types of BCR-ABL mutations present at treatment completion and when performed during treatment will be summarized by frequency tables.

Summaries of newly observed BCR-ABL mutations in patients post-baseline will be presented by visit.

Types of BCR-ABL mutations will be summarized using the modified as-treated population and as-treated population separately.

#### **6.4. Subset Analyses**

Subgroup analyses using Sokal score for MMR at 12 months (48 weeks) will be performed and two-sided 90% CIs will be presented. Sokal score will be categorized as follows:

- Low risk: Sokal score <0.8;
- Intermediate risk: Sokal score 0.8 to 1.2, and

- High risk: Sokal score >1.2.

This analysis will be evaluated for the modified as-treated population and the as-treated population, respectively.

## **6.5. Baseline and Other Summaries and Analyses**

Both as-treated population and modified as-treated population will be used unless otherwise specified. In case the as-treated population is completely the same as the modified as-treated population, summaries using the modified as-treated population may be omitted.

### **6.5.1. Baseline Summaries**

Baseline variables including the body weight and Ph status at the screening period will be summarized descriptively for both the modified as-treated population and the as-treated population according to [Section 5.2.1](#) and [Section 5.2.2.](#), respectively. The body mass index will be derived using the height and body weight at the screening period and will be reported as a baseline variable.

### **6.5.2. Study Conduct and Patient Disposition**

The total number of enrolled patients, the number of patients who completed/discontinued the treatment/study and the reason for any premature discontinuation from the treatment/study will be presented. In addition, the number of patients who completed the treatment to 12 months and discontinued the treatment within 12 months will be presented. The number of patients in each analysis set also be presented.

### **6.5.3. Study Treatment Exposure**

Exposure to study drug will be evaluated by duration of treatment exposure (the number of doses and missed doses) for as-treated population. In addition, actual dose intensity, and relative dose intensity will be evaluated. Descriptive statistics will be presented for continuous exposure variables: treatment duration (the number of days on treatment), actual dose intensity, and relative dose intensity. The frequency and percentage of patients with at least one dose reduction due to AE, temporally stopped study drug due to AE, reduction to 300 and 200 mg, and escalation to 500 and 600 mg will also be summarized. Further, the followings will be summarized:

- Number of dose delay;
- Number of dose reduction;
- Number of dose escalation;
- Time to the first dose delay;
- Duration of dose delay;
- Time to the first dose reduction;

- Duration of dose reduction, and
- Time to the first dose escalation.

Cumulative dose (unit: mg) will be calculated as the summation of all administered doses.

Duration of treatment will be calculated as

$$\text{Duration of Treatment (days)} = \text{DL} - \text{DF} + 1;$$

where

DL: the date of the last non-zero dose of the study drug, and

DF: the date of the first non-zero dose of the study drug.

Actual dose intensity (unit: mg/day) will be calculated as

$$\text{Actual dose intensity (mg/day)} = \text{aCD} / (\text{LDD} - \text{DF} + 1),$$

where

aCD: actual cumulative dose in mg;

LDD: the last dose date of zero or non-zero dose of the study drug, and

DF: the date of the first non-zero dose of the study drug.

Theoretical dose intensity (unit: mg/day) will be calculated as:

$$\text{Theoretical dose intensity (mg/day)} = \text{pCD} / (\text{LDD} - \text{DF} + 1).$$

where

pCD: planned cumulative dose (ie, cumulative starting dose) in mg;

LDD: the last dose date of zero or non-zero dose of the study drug, and

DF: the date of the first non-zero dose of the study drug.

Relative dose intensity will be calculate according the following formula:

$$\text{Relative dose intensity (\%)} = 100 \times (\text{Actual dose intensity}) / (\text{Theoretical dose intensity}).$$

#### **6.5.4. Concomitant Medications and Non-Drug Treatments**

Summary of concomitant medications will include the frequency and percentage of patients by Anatomical Therapeutic Chemical (ATC) Classification level 2 and preferred term. In case any specific medication does not have ATC classification level 2 coded term, it will be summarized under “Unavailable ATC classification” category.

Summary of non-drug treatments will include the frequency and percentage of patients by Medical Dictionary for Regulatory Activities (MedDRA) preferred term.

#### **6.5.5. Transfusions**

Summary of transfusions will include the frequency and percentage of patients by the transfusion type.

#### **6.5.6. ECOG Performance Status**

Summary of ECOG performance status will include the frequency and percentage of patients at each visit.

#### **6.5.7. Extramedullary Disease**

Summary of extramedullary disease will include the frequency and percentage of patients at each visit by body sites.

#### **6.5.8. Chest X-ray**

Results of chest X-ray will be summarized descriptively at each visit.

### **6.6. Safety Summaries and Analyses**

All safety analyses will be performed using the as-treated population.

#### **6.6.1. Adverse Events**

All AEs will be coded using the latest version of MedDRA dictionary at the analysis. The toxicity will be graded according to the National Cancer Institute Common Terminology Criteria for Adverse Events (NCI CTCAE), version 4.03.

The numbers of events and incidence rates will be tabulated by preferred term and system organ class. AEs will be presented with and without regard to causality. The frequency of overall toxicity, categorized by toxicity Grades 1 through 5, will be described. Additional tables will be provided for AEs that are observed with higher frequency.

AE summaries will include incidence of TEAEs by MedDRA preferred term and system organ class, incidence of clustered anemia/neutropenia/thrombocytopenia defined in [Appendix 2](#) and clustered leukopenia including PTs in leukopenia and white blood cell count decreased, SAEs including deaths, AEs that led to study drug discontinuation, characteristics of AEs that led to study drug discontinuation, AEs that led to study drug interruption, AEs that led to study drug reduction and AEs by maximum severity and relationship to study drug. Discontinuation due to AE and death data will also be listed.

AEs and AE categories including cardiac, oedema, effusion, gastrointestinal, diarrhea, nausea, vomiting, hemorrhage, anemia, neutropenia, thrombocytopenia, hypersensitivity, hypertension, infection, liver function, ALT, AST, myelosuppression, rash, renal and vascular will be summarized (see [Appendix 2](#)). A listing of AEs included in each AESI category will be provided by each patient.

TEAEs leading to death within 28 days of the last dose will be summarized.

Percentage of subjects with TEAEs (diarrhea, ALT, AST and the first onset of diarrhea) by maximum grade will be plotted using a cumulative bar chart at each month.

### **6.6.2. Laboratory Data**

Laboratory results including bone marrow aspirate will be classified according to the NCI CTCAE version 4.03. Laboratory results that are not part of NCI CTCAE or are impossible to be classified according to the NCI CTCAE using laboratory data only will be presented according to the categories: below normal limit, within normal limits and above normal limit (according to the laboratory normal ranges). Kidney Disease Improving Global Outcomes (KDIGO) categories (see [Appendix 1.5](#)) will be used for eGFR grading.

Laboratory assessments will be presented as mean changes from baseline and incidence of abnormal values. Shift tables will also be presented.

#### **6.6.2.1. Hy's Law**

Abnormal values in AST and/or ALT concurrent with abnormal elevations in total bilirubin that met the criteria outlined below in the absence of other causes of liver injury will be considered potential cases of drug induced liver injury (potential Hy's Law cases).

- Subjects with AST or ALT and total bilirubin baseline values within the normal range who subsequently presented with AST or ALT  $>3$  x upper limit of normal (ULN) concurrent with a total bilirubin  $>2$  x ULN with no evidence of hemolysis and an alkaline phosphatase  $<2$  x ULN or not available.
- For subjects with pre-existing ALT or AST or total bilirubin values above the ULN, the following threshold values were used in the definition mentioned above.

For subjects with pre-existing AST or ALT baseline values above the normal range: AST or ALT  $>2$  times the baseline values and  $>3$  x ULN, or  $>8$  x ULN (whichever was smaller).

For subjects with pre-existing values of total bilirubin above the normal range: Total bilirubin increased by 1 x ULN or  $>3$  x ULN (whichever was smaller).

The potential Hy's law will be confirmed at each time point. Further, an evaluation of drug-induced serious hepatotoxicity (eDISH) scatter plot of peak ALT, peak AST and peak ALT/AST versus peak total bilirubin will be presented.

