8.4.2. Potential Cases of Drug-Induced Liver Injury

Humans exposed to a drug who show no sign of liver injury (as determined by elevations in transaminases) are termed “tolerators,” while those who show transient liver injury, but adapt are termed “adaptors.” In some patients, transaminase elevations are a harbinger of a more serious potential outcome. These patients fail to adapt and therefore are “susceptible” to progressive and serious liver injury, commonly referred to as drug-induced liver injury (DILI). Patients who experience a transaminase elevation above 3 times the upper limit of normal (\times ULN) should be monitored more frequently to determine if they are an “adaptor” or are “susceptible.”

In the majority of DILI cases, elevations in aspartate aminotransferase (AST) and/or alanine aminotransferase (ALT) precede total bilirubin (TBili) elevations ($>2 \times$ ULN) by several days or weeks. The increase in TBili typically occurs while AST/ALT is/are still elevated above $3 \times$ ULN (ie, AST/ALT and TBili values will be elevated within the same lab sample). In rare instances, by the time TBili elevations are detected, AST/ALT values might have decreased. This occurrence is still regarded as a potential DILI. Therefore, abnormal elevations in either AST OR ALT in addition to TBili that meet the criteria outlined below are considered potential DILI (assessed per Hy’s Law criteria) cases and should always be considered important medical events, even before all other possible causes of liver injury have been excluded.

The threshold of laboratory abnormalities for a potential DILI case depends on the patient’s individual baseline values and underlying conditions. Patients who present with the following laboratory abnormalities should be evaluated further as potential DILI (Hy’s Law) cases to definitively determine the etiology of the abnormal laboratory values:

- Patients with AST/ALT and TBili baseline values within the normal range who subsequently present with AST OR ALT values $>3 \times$ ULN AND a TBili value $>2 \times$ ULN with no evidence of hemolysis and an alkaline phosphatase value $<2 \times$ ULN or not available;
- For patients with baseline AST **OR** ALT **OR** TBili values above the ULN, the following threshold values are used in the definition mentioned above, as needed, depending on which values are above the ULN at baseline:

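### SAP 6.6.2.1 requires AST/ALT and bilirubin to be high at the same time, so it omits the rare staggered case that the protocol still calls potential DILI; its other-causes clause is ambiguous

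*SAP*

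**What the plan says.** SAP 6.6.2.1 opens with a timing condition and a cause condition in one sentence: "Abnormal values in AST and/or ALT concurrent with abnormal elevations in total bilirubin that met the criteria outlined below in the absence of other causes". Values that satisfy both are classed as potential cases. The timing word appears again in the criterion for patients with normal baseline values (AST or ALT above 3×ULN, total bilirubin above 2×ULN, alkaline phosphatase below 2×ULN or unavailable, no haemolysis). The section then states that the potential Hy's "law will be confirmed at each time point". It gives no time window and does not say whether unscheduled samples count as time points. It also plans an eDISH "scatter plot of peak ALT, peak AST and peak ALT/AST versus peak total bilirubin will be presented".

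Protocol 8.4.2 uses essentially the same thresholds with wider timing. AST/ALT usually rises days or weeks before bilirubin, and typically "AST/ALT and TBili values will be elevated within the same lab sample". It then adds: "In rare instances, by the time TBili elevations are detected, AST/ALT values might have decreased. This occurrence is still regarded as a potential DILI". Rises separated by more than a few weeks are left to case-by-case clinical judgement.

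On cause, the protocol says that such cases "should always be considered important medical events, even before all other possible causes of liver injury have been excluded". A case meeting the laboratory criteria on repeat testing is potential so long as no other explanation has come to light. It becomes confirmed once the work-up is complete and alternatives are ruled out. Potential cases are reported as SAEs whatever the state of the work-up.

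**The concern.** The SAP's version history shows that this section was added in version 4 to assess liver injury in Japanese patients. One would expect its classification to follow the definition that sites use for reporting. As written, one patient can be a potential DILI and an SAE under the protocol, lie in the Hy's Law quadrant of the eDISH plot, and yet not be a case under the SAP rule. The SAP plans no reconciliation of the three.

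At stake is the reported number for the most serious kind of liver signal, in a trial small enough for one case to matter. The cause clause adds a second uncertainty: two analysts could apply it differently to the same patient and both claim to follow the SAP.

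**Working it through.** The plan states no figure on this point, so there is none to reproduce. The check compares the two definitions and then sizes one omitted case.

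**1. The two definitions side by side**
- *Thresholds:* essentially the same in both documents.
- *Timing:* the SAP requires both elevations together, judged at each time point. The protocol joins them without that requirement and explicitly keeps the case where AST/ALT has since fallen.
- *Cause:* the SAP requires absence of other causes and names no adjudicator or data source. The protocol separates none found so far (potential) from alternatives excluded (confirmed). The footnote to SAP 3.5.2 says direct and indirect bilirubin, which are part of the protocol's work-up, are not collected on the CRF. Part of the evidence on cause is therefore outside the analysis database.

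**2. Both rules applied to four hypothetical patients** (normal baseline, alkaline phosphatase 1×ULN throughout)

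| Patient | Protocol 8.4.2 | SAP, if all other causes must be excluded | SAP, if none known is enough | eDISH quadrant |
|---|---|---|---|---|
| A: ALT 4×, bilirubin 2.5× in one sample; cause not yet known | potential | no | yes | yes |
| B: ALT 5×, bilirubin 1×; 4 weeks later ALT 2×, bilirubin 2.5×; cause not yet known | potential | no | no | yes |
| C: as A, another cause found | not potential | no | no | yes |
| D: as A, all other causes excluded | counted | yes | yes | yes |

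Patient B is omitted by the SAP rule under either reading of the cause clause. Patient A is omitted only under the strict reading. Patient C is not a potential case under the protocol, so removing the cause clause altogether would create a new mismatch. Patient B assumes that 4 weeks falls within the protocol's undefined few weeks.

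**3. Size of one omitted case.** Assume 60 Ph+ patients plus about 3 Ph− patients are treated (protocol 9.1), so n = 63.
- One case: 1/63 = 0.0159, or 1.6%.
- No cases: exact one-sided 95% upper bound = 1 − 0.05^(1/63) = 0.046, or 4.6%.

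**4. How a staggered case could arise (assumption only).** Suppose ALT peaks at 10×ULN and halves every 7 to 10 days. It reaches 3×ULN after log2(10/3) = 1.74 half-lives, which is 1.74 × 7 = 12.2 days to 1.74 × 10 = 17.4 days. If the next sample came 4 weeks after the peak and was the first to show bilirubin above 2×ULN, the SAP rule would not count it. The peak, the half-life and the sampling gap do not come from the documents, and an intermediate sample could catch both values high.

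**The case against.** The other side has a good case. The SAP rule covers the pattern that protocol 8.4.2 calls typical and misses only the one it calls rare. The protocol asks for closer monitoring above 3×ULN and re-evaluation preferably within 48 hours, which makes a same-sample finding more likely. A staggered case would still appear in the eDISH plot, because peaks need not coincide. If reported, it would also reach the SAE summaries of SAP 6.6.1, and liver adverse events are summarised and listed by patient there. Periodic safety review adds another check. No test or decision depends on the classification. All of this stands as a limit on the size of the problem. None of it brings the rule into line with the protocol or explains a disagreement between displays.

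Three stronger readings are tempting, and the documents do not support them.
- A reader might infer that the SAP drops every case still unexplained. The protocol itself makes a case potential only while no other reason has been found, and the SAP clause can be read the same way. What is shown is ambiguity.
- A reader might infer that Table 2 of the protocol makes staggering more likely, since drug is interrupted above 5×ULN until recovery to 2.5×ULN or less. That shows a later bilirubin rise could meet a non-qualifying ALT. The documents give no recovery times and no frequency for the pattern.
- A reader might take the BELA figures (Grade 3/4 ALT elevation 23%, discontinuation for transaminase elevation 14%) as a guide to the number lost. They come from a 500 mg starting dose, against 400 mg here, and concern transaminases without bilirubin. Protocol 1.2.3 also reports no permanent liver injury or liver failure in that study.

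**Conclusion.** The timing mismatch is established from the text. Any count or listing built on SAP 6.6.2.1 omits the staggered case that protocol 8.4.2 retains, however the cause clause is read. The cause clause is a lesser defect: it blurs potential and confirmed cases, but it is not shown to lose unexplained ones.

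The expected effect is a small undercount in a descriptive safety display. Its frequency cannot be estimated from the documents. Each omitted case is worth 1.6 percentage points if 63 patients are treated, and it matters most when it changes one case to none. The primary endpoint is unaffected. The correction is worth making because it is cheap and because the section exists to describe liver injury in this population.

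**What to change.** Revise SAP 6.6.2.1 in three places.
1. **Timing.** Replace the concurrency requirement with: AST or ALT meets its threshold, and total bilirubin meets its threshold on the same day or within a prespecified window afterwards, unscheduled samples included. A window of 28 days is one reading of the protocol's few weeks; the protocol sets no number, so the sponsor should choose and state one. Say which sample supplies the alkaline phosphatase value. List longer separations for individual review, as protocol 8.4.2 provides.
2. **Cause.** Align the clause with the protocol's test for a potential case, that no other reason has been found so far, and name the data source. Reserve exclusion of other causes for confirmed cases. Do not simply delete the clause, because that would count explained cases.
3. **Reconciliation.** Show same-sample cases as a subset, and list each patient in the eDISH Hy's Law quadrant who is not counted, with the reason.

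The cost is SAP wording and a small programming change. The timing change needs no new data. The reported number of potential cases may be slightly higher, and some may later prove to have another cause.
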